## **7.8.2 Adverse Events**

AEs will be coded with the most recent version of MedDRA coding dictionary. Patients will be analysed according to the actual treatment received.

Any clinically significant new finding in the physical examination, vital signs (blood pressure and pulse symptoms) and in the 12-lead ECG starting after visit 2 will be considered as an AE and will be reported as such.

The analyses of AEs will be descriptive in nature. All analyses of AEs will be based on the number of patients with AEs and not on the number of AEs.

#### 7.8.2.1 Assignment of AEs to treatment

In general, the analysis of AEs will be based on the concept of treatment emergent AEs. That means that all AEs occurring between first drug intake till 7 days (residual effect period – REP) after last drug intake will be assigned to the on-treatment period. All AEs occurring before first drug intake will be assigned to ‘screening’ and all AEs occurring after last drug intake + REP of 7 days will be assigned to ‘follow-up’ (for listings only). For details on the treatment definition, see [Section 6.1](#).

If only the start date of an AE is collected (without the start time), any AE occurrence on the same day as the first avenciguat administration will be assigned to the on-treatment phase.

In general, tables will only present AEs assigned to the first treatment taken except drug-related AEs which will be presented as actual treatment taken at each given timepoint. AEs and serious adverse events (SAEs) assigned to the following phases: screening, on-treatment, post-treatment will be listed.

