### 5.2.6 Assessment of adverse events

#### 5.2.6.1 Definitions of AEs

##### 5.2.6.1.1 Adverse event

An AE is defined as any untoward medical occurrence in a patient or clinical investigation subject administered a medicinal product and which does not necessarily have to have a causal relationship with this treatment.

An AE can therefore be any unfavourable and unintended sign (including an abnormal laboratory finding), symptom, or disease temporally associated with the use of a medicinal product, whether considered related or not.

The following should also be recorded as an AE in the eCRF and BI SAE form (if applicable):

- worsening of the underlying disease or of other pre-existing conditions changes in vital signs, ECG, physical examination and laboratory test results, if they are judged clinically relevant by the Investigator

If such abnormalities already exist prior to trial inclusion, they will be considered as baseline conditions and should be collected in the eCRF only.

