### 5.2.6.2 Adverse event collection and reporting

#### 5.2.6.2.1 AE collection

The investigator shall maintain and keep detailed records of all AEs in the patient files. The following must be collected and documented on the appropriate CRF(s) by the investigator:

- From signing the informed consent onwards until the individual patient's end of trial (= the End of Study (EoS) visit):  
all AEs (serious and non-serious) and all AESIs.
- After the individual patient's end of trial:  
the investigator does not need to actively monitor the patient for new AEs but should only report any occurrence of cancer and trial drug related SAEs and trial drug related AESIs of which the investigator may become aware of by any means of communication, e.g. phone call. Those AEs should be reported on the BI SAE form (see [section 5.2.6.2.2](#)), but not on the CRF.

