### **7.2.6      Safety analyses**

Adverse events will be coded using the Medical Dictionary for Drug Regulatory Activities (MedDRA). Standard BI summary tables and listings will be produced. All adverse events with an onset between start of treatment and end of the REP, a period of 7 days after the last dose of trial medication, will be assigned to the on-treatment period for evaluation.

[figure not shown]
Safety analyses will be done by “treatment at onset” principle. All treated patients will be included in the safety analysis. In general, safety analyses will be descriptive in nature and will be based on BI standards. No hypothesis testing is planned.

Statistical analysis and reporting of adverse events will concentrate on treatment-emergent adverse events, i.e. all adverse events occurring between start of treatment and end of the REP. Adverse events that start before first drug intake and deteriorate under treatment will also be considered as ‘treatment-emergent’.

Frequency, severity, and causal relationship of adverse events will be tabulated by system organ class and preferred term after coding according to the current version of the Medical Dictionary for Drug Regulatory Activities (MedDRA) at database lock.

Laboratory data will be analysed both quantitatively as well as qualitatively. The latter will be done via comparison of laboratory data to their reference ranges. Values outside the reference range as well as values defined as clinically relevant will be summarised. Treatment groups will be compared descriptively with regard to distribution parameters as well as with regard to frequency and percentage of patients with abnormal values or clinically relevant abnormal values.

Vital signs, physical examinations, or other safety-relevant data observed at screening, baseline, during the course of the trial and at the end-of-trial evaluation will be assessed with regard to possible changes compared to findings before start of treatment.

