**4. CHANGES IN THE PLANNED ANALYSIS OF THE STUDY**

There are no changes in this TSAP compared to the statistical methods described in the CTP.

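### SAP 7.8.2.1 defines treatment-emergent AEs by time of occurrence only and omits the protocol's rule that an AE starting before first dose also counts if it worsens on treatment

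*SAP*

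**What the plan says.** Protocol 7.2.6 sets a window and then widens the definition. The window covers "All adverse events with an onset between start of treatment and end of the REP, a period of 7 days after the last dose". The reporting of AEs is then to concentrate on treatment-emergent events, and for these the protocol adds: "Adverse events that start before first drug intake and deteriorate under treatment will also be considered as" treatment-emergent.

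SAP 7.8.2.1 bases the AE analysis on the treatment-emergent concept and explains it by timing alone: "That means that all AEs occurring between first drug intake till 7 days" after last intake belong to the on-treatment period. For earlier events it says "All AEs occurring before first drug intake will be assigned to" screening. The only relief near first dose concerns events with a start date but no start time: "any AE occurrence on the same day as the first avenciguat administration will be assigned to the on-treatment phase".

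SAP section 4 reads: "There are no changes in this TSAP compared to the statistical methods described in the CTP".

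**The concern.** The SAP is the document from which the AE tables will be programmed. Read literally, it keeps a screening-onset AE in the screening phase whatever happens to it after dosing, where the protocol would count it once it deteriorates.

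Such events are plausible in this trial. AEs are collected "From signing the informed consent onwards until the individual" patient's end of trial (Protocol 5.2.6.2.1). Screening may last up to 6 weeks and includes HVPG measurement and, where needed, gastroscopy. Protocol Table 1.4.2:3 lists nausea, vomiting, irregular heartbeat and abdominal discomfort among the effects of those procedures. Table 1.4.2:1 lists hypotension, tachycardia, oedema and gastrointestinal events as potential effects of BI 685509. The two lists overlap, so a symptom could begin in screening and worsen during up-titration. Safety and tolerability are among the main objectives (Protocol 2.1.1), and there is no placebo arm (Protocol 3.2) against which to judge the on-treatment frequencies.

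**Working it through.** The check is a comparison of rules. The documents give no rate of pre-dose AEs or of their worsening, so no affected count can be computed and there is no planned figure to reproduce.

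**Step 1: the two rules by type of event**

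| Event | Protocol 7.2.6 | SAP 7.8.2.1 |
|---|---|---|
| Onset from first dose to last dose + 7 days | Treatment-emergent | On-treatment |
| Onset on the day of first dose, no start time | Not addressed | On-treatment |
| Onset before first dose, does not worsen | Not treatment-emergent | Screening |
| Onset before first dose, worsens on treatment | Treatment-emergent | Screening |

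The rules conflict in the last row only.

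**Step 2: is the missing rule restored elsewhere in the SAP?** The phase definitions (6.1), the time windows (6.7) and the remaining AE sections (7.8.2 and 7.8.2.2 to 7.8.2.5) contain no worsening clause. SAP 7.8.2 treats clinically significant new findings after Visit 2 as AEs; that does not cover the worsening of an event already open.

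**Step 3: how much worsening is caught by recording rules?** Protocol 5.2.6.1.1 requires "worsening of the underlying disease or of other pre-existing conditions" to be recorded as an AE. Protocol 6.2.1 includes new clinically relevant findings from the screening period among baseline conditions. Where a screening finding is held as a baseline condition, its worsening should therefore appear as an AE, presumably with an on-treatment onset that the SAP already counts. But Protocol 5.2.6.2.1 also collects AEs, as AEs, from consent. Nothing in either document says that such an AE receives a new record or a new onset date when it worsens. The remaining exposed set is AEs open in screening that worsen on treatment without a new record.

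**Step 4: direction.** The SAP's set of on-treatment events equals the protocol's set less that exposed set. Patient counts can only be equal or lower. The tables by maximum CTCAE grade (SAP 7.8.2.3) would also miss the higher grade.

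**Step 5: scale, for illustration only.** In a group of exactly 20, one patient is 1/20 = 5 percentage points. SAP Table 6.1:1 shows two treatment labels. If the monotherapy groups were pooled, with 80 patients in total and 20 in group 4, one patient would be 1/(80 − 20) = 1/60 ≈ 1.7 points. In either case the row changes only if that patient has no other on-treatment AE in it, because AE analyses count patients rather than events (SAP 7.8.2).

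**The case against.** The best defence is continuity. SAP section 3 presents the SAP as an elaboration of protocol section 7 and assumes the reader knows the protocol; section 4 declares no change. On that view the worsening clause still applies and SAP 7.8.2.1 merely restates the protocol's onset window, opening with a general qualifier. This would be persuasive if the SAP were silent. It is not: it explains treatment-emergent by timing and then disposes of all pre-dose AEs. A programmer would have two conflicting instructions.

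A second defence is that SAP 7.8 and 7.8.2.3 defer to company standards that may contain the rule. That is possible and cannot be checked from the documents, but it would not remove the contrary wording in the trial's own SAP.

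A third is limited impact. Baseline conditions are covered as described in step 3, patients with a history of clinically relevant orthostatic hypotension are excluded (Protocol 3.3.3, criterion 15), and vital signs are analysed separately, including minimum values (SAP 7.8.3). This stands, and it keeps the point modest.

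A reader might also infer more than the documents support:
- That every pre-dose AE is sent to screening. The same-day rule is an exception.
- That screening AEs are expressly confined to listings. The parenthesis to that effect follows the follow-up phase and may apply to it alone.
- That these events vanish from the report. SAP 7.8.2.1 says screening-phase AEs and SAEs will be listed.
- That any worsening symptom would be lost. Some will be recorded as a new AE.

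**Conclusion.** The conflict is established by the text: SAP 7.8.2.1 omits a protocol rule, says the contrary for pre-dose AEs, and no change is declared. It should be corrected before the AE tables are produced. Its reach is limited to AEs already open in screening that worsen between first intake and last intake + 7 days without a new AE record. How many there will be cannot be derived, and a fixed loss of 5 percentage points per patient should not be inferred, since it needs a denominator of exactly 20 and no other AE in the same row. The bias runs one way, towards equal or lower treatment-emergent counts. The conclusion assumes that the unseen company guidance does not override the SAP text and that sites do not routinely open a new record when a screening AE worsens. If they do, the practical loss shrinks towards nil, but the inconsistency remains.

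**What to change.** Add to SAP 7.8.2.1: AEs with onset before first intake that worsen between first intake and last intake + 7 days, shown by a higher CTCAE grade or by a new AE record for the worsening, are treatment-emergent and tabulated as on-treatment, as in Protocol 7.2.6.

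The protocol has intensity recorded as a CTCAE grade but does not say whether a change of grade within one record is dated. The team should confirm which of the two indicators the data can support.

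If the narrower definition is intended, declare and justify it in SAP section 4 instead. The cost is one SAP sentence and one derivation flag; design, sample size and efficacy analyses are unaffected.

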#### 7.8.2.2 Analysis of other significant AEs

Other significant AEs will be reported and summarised according to ICH E3 criterion [\(5\)](#). Thus, AEs classified as ‘other significant’ will include those non-serious adverse events with ‘action taken = discontinuation’ or ‘action taken = dose reduced’.

#### 7.8.2.3 AE summaries

An overall summary of adverse events will be presented.

The frequency of patients with adverse events will be summarised by treatment, primary SOC and PT. The SOC will be sorted by frequency, PTs will be sorted by frequency (within SOC). AEs which were defined as secondary endpoints will be summarised separately. AEs will also be reported by intensity according to the maximum Common Terminology Criteria for Adverse Events (CTCAE). Separate tables will be provided for patients with other significant AEs according to ICH E3 [\(5\)](#), adverse events of special interest (AESI), for patients with serious adverse events, for patients with AEs leading to discontinuation, for patients with AEs leading to dose reduction, for patients with drug-related AEs and for patients with fatal AEs. Note that for drug-related AEs, separate tables will be prepared for treatment group 4 – one for AEs related to avenciguat and one for AEs related to empagliflozin. A listing of AEs related to study procedure will be prepared based on enrolled set.

For further details on summarisation of AE data, please refer to “Handling of missing and incomplete AE dates” [\(2\)](#) and “Analysis and Presentation of Adverse Event data from Clinical Trials” [\(6\)](#).

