- patients with a QT or QTcF interval > 500 ms, or an increase of QT or QTcF of > 60 ms from the pre-dose value at Visit 2 / enrolment (baseline). Such cases must be reported as AEs
- the patient can no longer receive trial medication for other medical reasons such as surgery, AEs, other diseases
- the patient has not successfully completed the dose titration period (i.e. Visit 4), but has persistent AEs or severe effects requiring down-titration of the trial medication (refer to [Section 4.1.4.1](#))
- a female patient becomes pregnant. The patient will be followed up until birth or otherwise termination of the pregnancy. The data of the patient will be collected and reported in the Clinical Trial Report (CTR) until last patient last visit and any events thereafter will be reported in the BI Pharmacovigilance (PV) database (refer to [Section 5.2.6.2.3](#))

Trial-specific procedures have also been defined for Investigators to follow in case of increased liver enzymes (AST, ALT, and total bilirubin) after enrolment. For details refer to [Section 5.2.6.1.4](#) and [Appendix 10.2 \(P09-12413\)](#).

In the event of intolerance to BI 685509 after successful completion of the dose titration period at Visit 4 (e.g. persistent AEs despite two down-titrations, or severe effects at any dose), permanent treatment discontinuation should also be considered, based on Investigator judgement (refer to [Section 4.1.4.1](#)).

In addition to these criteria, the Investigator may discontinue patients at any time based on clinical judgement.

If a patient permanently discontinues the trial medications before the last allocated dose, an Early Discontinuation (ED) visit is required ideally within 7 days of discontinuing the medication. An EoS visit should be performed 4 weeks after the ED visit. Refer to Sections [6.2.2.1](#) and [6.2.3](#) for further details, including guidance with respect to trial assessments that should be included as part of an ED visit.

An individual patient will permanently discontinue empagliflozin if:

- Ketoacidosis is suspected.
- Fournier's gangrene is suspected.

If a patient in treatment arm 4 permanently discontinues empagliflozin or BI 685509, the patient must permanently stop the treatment with the other trial medication as well.

In the following cases, empagliflozin must be interrupted:

- Complicated UTI, including urosepsis
- Symptomatic volume depletion

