#### 4.1.4 Drug assignment and administration of doses for each patient

Trial medication will be dispensed at the investigational sites in accordance with the [Flow Chart](#). At dispensing visits patients will be given the appropriate number of medication kits for BI 685509 (range 1-2) and empagliflozin (range 1-2) depending on the interval between the visits (for further kit details refer to [Section 4.1.6](#)). The last dose of BI 685509 will be administered in the evening of the day before the EoT visit and the last dose of empagliflozin in the morning of the day before the EoT visit.

All patients will start on a dose of [REDACTED] BI 685509 *BID* at Visit 2. Treatment group 4 will receive a fixed dose of 10mg empagliflozin *QD* in addition. 7 days later, at Visit 3, and again at Visit 4, 7 days after Visit 3, all patients will be up-titrated to a dose of [REDACTED] BI 685509 *BID*, and then to the maintenance dose of [REDACTED] BI 685509 *BID*.

Patients will be informed of the dose titration period and will be made aware that up-titration for BI 685509 is being used. If a patient does not tolerate an up-titration, e.g. due to orthostatic dysregulation, the rules in [Section 4.1.4.1](#) must be followed. From Visit 4 onwards, patients of the treatment group 1, 2, 3 and 4 will continue to receive the maximum dose of [REDACTED] BI 685509 (plus 10mg empagliflozin *QD* for group 4 only) until reaching the EoT visit (8 weeks after starting the trial medication).

If a patient has an AE that, based on Investigator judgement, may be related to BI 685509 or empagliflozin, the trial medication can either be:

- interrupted (i.e. the trial medication is stopped, and subsequently re-started. The up-titration approach described above is followed.)

OR

- the dose can be reduced (down-titrated) for BI 685509 if the patient has successfully completed the dose titration period (i.e. Visit 4). No dose reduction is allowed for empagliflozin.

For further details refer to Sections [4.1.4.1](#) and [4.1.4.2](#).

All trial medication assignments, including up / down-titrations for BI 685509 and provision of replacement kits, will be managed through the IRT system. Down-titrations of BI 685509 must not be performed by instructing the patient to take less than the two daily doses (refer to [Section 4.1.4.1](#)).

Table 4.1.4: 1 Drug assignment and dosage by treatment group

Randomisation Allocation	Week 1 of Treatment	Week 2 of Treatment	Week 3 of Treatment Onwards

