#### 4.1.4.1 Rules for down-titration in case of intolerance to BI 685509

If a patient has an AE that, based on Investigator judgement, may be related to trial medication, the down-titration rules below must be followed. These rules apply if the patient has successfully completed the dose titration period (i.e. Visit 4) and is either still taking their final assigned dose of trial medication, or if they have missed  $\leq 3$  consecutive doses. If the patient has not successfully completed the dose titration period (i.e. Visit 4), down-titration is not permitted; in case of persistent AEs or severe effects, the patient must permanently discontinue treatment (refer to [Section 3.3.4.1](#)).

- if the patient is receiving [REDACTED] BID BI 685509 the dose will be down-titrated one level to [REDACTED] BID BI 685509

Once down-titration has taken place, no further up-titration will be permitted.

If a patient continues to have an AE, or a new AE develops, that based on Investigator judgement, may be related to trial medication, a second down-titration will be permitted:

- if the patient is receiving [REDACTED] BID BI 685509 the dose will be down-titrated to [REDACTED] BID BI 685509

Down-titration must not be performed by taking less than the two daily doses or by splitting tablets so that a whole tablet is not taken. Down-titration will be managed through the IRT system (refer to [Section 4.1.4](#)). After the successful completion of the dose titration period (i.e. Visit 4), in case of persistent AEs despite down-titration, or severe effects at any dose, permanent treatment discontinuation should be considered (refer to [Section 3.3.4.1](#)). Patients who are down-titrated will need to return to the investigational site to receive their continuing supply of trial medication, either at the next scheduled visit or via an unscheduled visit.

 One dose refers to an individual time point e.g. morning dose or evening dose.

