## **7.7 EXTENT OF EXPOSURE**

A descriptive statistics table with mean, SD, median and range of the number of days a patient was on treatment will be provided for the treated set. The tables will also provide the sum total of the time that all patients pooled together were on treatment. A separate listing will be created for patients who switched treatment, had dose interruption or dose down-titration any time indicating exposure to each treatment.

A frequency table of number and percent of patients belonging to each categorical range of exposure weeks will be provided as well. The following are the categories of exposure-ranges (in weeks): “0 to 4 weeks”; “> 4 to 8 weeks” and “>8 weeks”.

No temporary treatment interruption period will be reported.

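### The AE action-taken tables and the exposure summary leave out treatment interruption, which before Visit 4, and throughout for empagliflozin, is the only dosing change short of stopping for good

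*SAP*

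**What the plan says.** **SAP, AE summaries.** Section 7.8.2.3 lists tables by SOC and PT, by intensity and for drug-related AEs, the last split by drug in group 4. It adds separate tables "for patients with AEs leading to discontinuation, for patients with AEs leading to dose reduction". Section 7.8.2.2 defines other significant AEs as non-serious AEs with "action taken = discontinuation" or "action taken = dose reduced". Interruption is in neither place.

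**SAP, exposure.** Section 7.7 summarises days on treatment and lists patients who switched treatment, were interrupted or were down-titrated. It ends: "No temporary treatment interruption period will be reported".

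**Protocol, responses to a related AE.** Section 4.1.4 gives two options short of stopping for good. Trial medication may be "interrupted (i.e. the trial medication is stopped, and subsequently re-started", or the BI 685509 dose may be reduced once the patient has completed titration at Visit 4. For the other drug, "No dose reduction is allowed for empagliflozin". Before titration is complete, section 4.1.4.1 says "down-titration is not permitted; in case of persistent AEs or severe effects, the patient must permanently discontinue treatment". Section 3.3.4.1 states "In the following cases, empagliflozin must be interrupted", and names complicated UTI (including urosepsis) and symptomatic volume depletion.

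**The concern.** Safety and tolerability are a main objective (Protocol 2.1.1), and Protocol 3.2 describes orthostatic dysregulation as dose-limiting. Tables of AEs by action taken are where a reader looks to see how often AEs forced a change in dosing. These tables cover two of the three actions that the protocol provides for, and the omitted one is the only non-permanent action available in two settings of interest: the up-titration phase in every group, and empagliflozin in group 4.

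Interruption is not a minor event here. Under Protocol 4.1.4.2, a patient who misses more than 3 consecutive doses goes back to the starting dose and must take each step for at least 7 consecutive days before moving up. A single interruption of that kind can cost as much time below the maintenance dose as the whole initial titration. The SAP already treats interruption and down-titration alike for efficacy, since section 7.4.4 excludes both from the supplementary analysis, but for safety only down-titration gets a table.

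**Working it through.** No planned figure depends on this point, so there is none to reproduce. The check sets the protocol's permitted actions against the SAP's planned summaries, with simple arithmetic from the visit days in the Flow Chart.

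**Inputs.** Visit 2 (first dose) is Day 1, Visit 4 is Day 15 and EoT is Day 57, with the last dose on the day before EoT.

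**Step 1: days on which dose reduction is unavailable (nominal schedule).**
- Planned treatment days: 57 − 1 = 56.
- BI 685509, before Visit 4: 15 − 1 = 14 days; 14/56 = 25%.
- Empagliflozin: 56/56 = 100%.

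**Step 2: permitted change and planned action-taken table.**

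| Setting | Permanent stop | Dose reduction | Interruption |
|---|---|---|---|
| BI 685509 before Visit 4 | allowed, tabulated | not allowed | allowed, no table |
| BI 685509 from Visit 4 | allowed, tabulated | allowed, tabulated | allowed, no table |
| Empagliflozin (group 4), all days | allowed, tabulated | not allowed | allowed (required in two cases), no table |

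Holding a patient at the current step (Protocol 4.1.4.2) follows from the 7-day rule after an interruption; it is not a separate response to an AE. In the first and third rows, therefore, an AE that changes dosing without ending treatment can only be an interruption. The missing table concerns all 56 days for both drugs. The 14 days mark only the period in which BI 685509 has no tabulated alternative short of discontinuation.

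**Step 3: what a restart costs.** There are two up-titration steps of at least 7 days each: 2 × 7 = 14 days at least below the maintenance dose, plus the days off drug. Against 56 planned days this is at least 25%.

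**Step 4: could another planned summary fill the gap?**
- *Exposure (SAP 7.7):* a patient listing, with no stated link to the AE and no time off drug.
- *Compliance (SAP 7.2):* Yes, No or Missing per visit. The denominator in Protocol 4.3 is the number of tablets the investigator directed, so an investigator-directed interruption need not lower it.
- *Intercurrent events (SAP 6.3, counted under 7.4.1):* premature discontinuation is included, interruption is not.
- *Supplementary analysis (SAP 7.4.4):* removes interrupted patients, but together with down-titrated patients and for efficacy only.
- *User-defined AE categories (SAP 7.8.2.5):* hypotension and syncope are summarised whatever the action taken. No category is defined for UTI or volume depletion, the two triggers for mandatory empagliflozin interruption.

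None of these gives the number of patients with an AE leading to interruption, or the time off drug.

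**The case against.** The strongest reply is that no AE disappears. Each treatment-emergent AE enters the SOC/PT and intensity tables and, where applicable, the drug-related, serious and special-interest tables. Empagliflozin-related events in group 4 are shown by drug. Hypotension and syncope have patient-based and event-based summaries and also feed two secondary endpoints. Persistent AEs or severe effects during titration require permanent discontinuation, which is tabulated, so the gap is confined to events managed by stopping and restarting. With about 20 patients per group and no hypothesis tests, listings may be enough to review a few interruptions. All of this stands, and it limits the point to a missing summary.

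A reader might go further and infer that dose-limiting intolerance is under-reported, or that the treatments will look better tolerated than they were. The documents do not support that: the events are reported, and only one attribute of them lacks a summary. Nor can a count of affected patients be given, because no interruption rate is stated and some interrupted patients may later be down-titrated or discontinued and so be captured.

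The sponsor's AE reporting standard, cited in SAP 7.8.2.3, might include an interruption display, but its content is not in the documents. That does not settle the matter: the section names its tables without this one, and section 7.7 expressly excludes interruption periods. Finally, the SAP ties other significant AEs to an ICH E3 criterion, and nothing in the documents shows that this criterion calls for interruption. That definition can stay.

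**Conclusion.** The point holds as a reporting gap that is cheap to close. AEs are summarised by action taken only for discontinuation and dose reduction, and the exposure summary leaves out time off drug. As a result, no planned summary shows how often AEs forced an interruption or how long it lasted. The gap covers the whole treatment period. It matters most where interruption is the only dosing change short of discontinuation: 14 of 56 planned days (25%) for BI 685509 in all groups, and all 56 days for empagliflozin in group 4, which has a minimum of 20 patients.

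The primary estimate and the secondary endpoints are unaffected. The conclusion assumes the nominal visit schedule and that the tables named in the SAP are the ones produced. The size in patients is unknown.

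**What to change.** **SAP 7.8.2.3:** add one table of patients with AEs leading to interruption, by treatment group and PT, with a count of those with onset before Visit 4. Split it by drug in group 4 if the eCRF records action taken for each drug.

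**SAP 7.7:** replace the sentence "No temporary treatment interruption period will be reported" with a commitment to give the number of patients interrupted and the days off drug per group. Separate AE from non-AE reasons where recorded, because interruptions also arise from compliance (Protocol 4.1.4.2) and from restricted co-medication (Protocol 4.2.2.1).

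Leave SAP 7.8.2.2 as it is, and change no dosing or interruption rule.

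**Cost:** SAP wording, one extra table with small cell counts, and one exposure line. The SAP already needs to identify interrupted patients for sections 7.4.4 and 7.7. Whether interruption is recorded against each AE, and separately for each drug, is not shown in the documents and should be checked against the eCRF before the wording is fixed.
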